5.4 Accountability of Investigational Products

Fisher & Paykel® will provide technical and educational support for the duration of the trial.

5.5 Concomitant Medications and Medical Treatments

Patients on asthma prevention or treatment medications are excluded from this trial due to the confounding effects of existing asthma and its required management. The clinician will use medical treatments such as beta-2 agonist, systemic steroid, and hypertonic saline.

6. SAFETY AND ADVERSE EVENT(S)

During the study, AEs, regardless of relatedness to the study device, will be reported on the AE page of the CRF (Appendices 4). All adverse reactions will be recorded in CRF and registered in the manuscript and clinicaltrial.gov. Open disclosure is paramount to the ongoing efficacy and ethical conduct of the trial, so parents/ legal guardians of participants experiencing AE are to be entirely briefed about the nature and effect of the AE. They are to be informed of likely consequences and alternative facts considered relevant following the standard disclosure duty.

6.1 Definitions and Classification

✓ **Adverse Event (AE)**

Any untoward medical occurrence in a patient who is administered a pharmaceutical product or device does not necessarily have a causal relationship with this treatment. An AE is any unfavorable and unintended sign (including an abnormal laboratory finding), symptom, or disease temporally associated with the use of an investigational product.

✓ **Suspected Adverse Reaction**

Suspected adverse reaction means any adverse event for which there is a reasonable possibility that the drug caused the adverse event. For IND safety reporting purposes, 'reasonable possibility' means there is evidence to suggest a causal relationship between the drug and the adverse event. A suspected adverse reaction implies less certainty about causality than an adverse reaction, which means any adverse event caused by a drug.

✓ **Adverse Reaction**

An adverse reaction means any adverse event caused by a drug. Adverse reactions are a subset of all suspected adverse reactions where there is reason to conclude that the drug caused the event.

✓ **Unexpected Adverse Reaction**

An adverse event or suspected adverse reaction is considered as unexpected;

- ✓ Not listed in the investigator brochure or is not listed at the specificity or severity that has been observed
- ✓ An investigator brochure is not required or available
- ✓ Not consistent with the risk information described in the general research plan or elsewhere in the current application, as amended.
 - For example, under this definition, hepatic necrosis would be unexpected (under greater severity) if the investigator brochure referred only to elevated hepatic enzymes or hepatitis.

- Similarly, cerebral thromboembolism and cerebral vasculitis would be unexpected (under greater specificity) if the investigator brochure listed only cerebral vascular accidents.
- ✓ Unexpected as used in this definition, it also refers to adverse events or suspected adverse reactions mentioned in the investigator brochure as occurring with a class of drugs or as anticipated from the drug's pharmacological properties, but are not explicitly mentioned with the drug under investigation.

✓ Serious Adverse Reaction

An adverse event or suspected adverse reaction is considered "serious" if, in the view of either the investigator or sponsor, it results in any of the following outcomes: Death, a life-threatening adverse event, inpatient hospitalization or prolongation of existing hospitalization, a persistent or significant incapacity or substantial disruption of the ability to conduct normal life functions, or a congenital anomaly/congenital disability. Important medical events that may not result in death be life-threatening, or require hospitalization may be considered serious when, based upon appropriate medical judgment, they may jeopardize the patient or subject and may require medical or surgical intervention to prevent one outcome listed in this definition. Examples of such medical events include allergic bronchospasm requiring intensive treatment in an emergency room or at home, blood dyscrasias or convulsions that do not result in inpatient hospitalization, or the development of drug dependency or drug abuse.

✓ Life-Threatening Adverse Reaction

An adverse event or suspected adverse reaction is considered "life-threatening" if, in the view of either the investigator or sponsor, its occurrence places the patient or subject at immediate risk of death. It does not include an adverse event or suspected adverse reaction that, had it occurred in a more severe form, might have caused death.

6.2 Follow-up 15 days safety assessment

On the initial business day after 15 days, post-discharge an investigator will contact the parent/legal guardian to ask about any AE which may have occurred following the infant's return home under any medical administrations' requirements.

7. STATISTICAL METHODS

7.1 Sample Size

Sample size calculations were done using a t-test on the primary outcome. Based on our pilot trial to obtain a power of 80% and alpha of 0.05 with a 1:1 proportion of control to intervention groups, the sample size yielded a total of 100 participants for CRS, 38 for RR, and 43 for HR. Given these sample sizes, we chose to recruit a minimum of 100 subjects. However, the final sample size was 110 patients, considering the study's longitudinal aspect (with a 10% attrition rate).

7.2 Data Analysis Methods

Categorical and continuous variables will be expressed as frequency (percentage) and median (IQR). Between groups, we will use the Mann-Whitney-U test for comparing the time of success for HR, RR, and CRS (SPSS Inc., version 25.0, Chicago, IL, USA). The longitudinal analysis part of the study will be performed non-parametrically with the Brunner Langer model for CRS conducted with a linear mixed model in a parametric way for HR and RR. Brunner Langer model (F1-LD-F1) is applied using web-based software (R software, version 3.5.2, package: nparLD, R Foundation for Statistical Computing, Vienna, Austria; <http://r-project.org>). The PROC MIXED procedure in the SAS software is used (Version 9.3; SAS Institute, Cary, NC, USA) to perform linear mixed models in which subjects will be included as random effects. When there is a significant interaction effect in the longitudinal analysis ($P < .1$), the time effect will be analyzed in each group, and groups will be compared at baseline and following time points (the baseline was subtracted from these time points). The proportions of the treatment failure at 4 hours, rescued patient, ICU admission, and AE are analyzed using Fisher's Exact test and given with odds ratio (OR) and 95% Confidence Interval (CI). We will perform intention-to-treat and per-protocol approaches for all outcomes. The time of success for HR, RR, and CRS outcomes will be analyzed using the PP approach. A 2-sided $P < .05$ defines statistical significance.

Statistical Analysis Plan

The biostatistician in the study, which has blinded to allocation, will perform the analysis. An interim analysis will not be performed. If substantial evidence of increased risk of harms ($p < 0.001$) observed in both groups, stopping rules will be used with the biostatistician's advice. Intention to treat and per-protocol approaches will be conducted if necessary.

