Heart rate (beat per min)†	X	X	X	X	X	X	X	X	X	
Respiratory rate (breath per min)†	X	X	X	X	X	X	X	X	X	
Arterial blood pressure (mmHg)†	X	X	X	X	X	X	X	X	X	
Clinical respiratory score†	X	X	X	X	X	X	X	X	X	
PCR	X									
Blood sample*	X									
VBG*	X			X						
Concomitant Medications	X	X	X	X	X	X	X	X	X	
Medical treatment‡	X	X	X	X	X	X	X	X	X	
Adverse event record	X	X	X	X	X	X	X	X	X	

If the patient was not discharged after 96 hours, the procedures mentioned above were continued.

†All parameters were measured during the resting of children.

*Samples were performed at any time if the clinician deemed it necessary.

Protocol No 1
Date: 10/03/2017
Revised 1: 10/03/2020
Revised 2:14/02/2021

**All children included in the study were phoned after 15 days post-discharge.

†The clinician decides to use medical treatments such as beta2 agonist, systemic steroid, and hypertonic saline.

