2.2 Primary Objectives

- ✓ The median time it takes for HR to reach its normal range for age (hour)
- ✓ The median time it takes for RR to reach its normal range for age (hour)
- ✓ The median time it takes for CRS to regress from severe [scores of 9-12] to moderate [scores of 5-8] bronchiolitis, or from moderate [scores of 5-8] to mild [scores of 0-4] bronchiolitis (hour)

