2.3 Secondary Objectives

- ✓ The mean difference in HR decreased compared with the baseline value from randomization to 96 hours (or to discharge)
- ✓ The mean difference in RR decreased compared with the baseline value from randomization to 96 hours (or to discharge)
- ✓ The mean difference in CRS regress compared with the baseline value from randomization to 96 hours (or to discharge)
- ✓ The length of hospital stays [from admission to discharge (hour)]
- ✓ The length of oxygen treatment [from admission to weaning to room air (hour)]

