4.2 Follow up

An investigator will attend telephone follow-up on the first working day after the infant is 15 days post-discharge. The parent/legal guardian will be contacted and asked 7 set survey questions to determine whether an adverse event under therapeutic goods administration requirements, and the treatment has been successful post-discharge (Appendix 2). The investigator will record any identified adverse events relating to the study devices, and the infant will be followed up further if it is clinically indicated.

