5.1 Investigational Treatments

Children will receive maximum therapy for 4 hours, which means that children receive at a flow rate of 2 L*kg/min, but we will let the FiO₂ reduce if children give an excellent response to the treatment. For children on St-FMOT, the FiO₂ will be reduced at any time if children provide a suitable response to the treatment, and the oxygen requirement will be controlled by turning off the flow every hour. Reducing the flow rate should be considered after 4 hours if the children's observations for HR, RR, retraction, SpO₂, feeding ability and tolerability, CRS, and PEWS stabilize or decrease.

➤ **Control Arm:** Children in the standard-therapy group received supplemental oxygen via a simple face mask, a range of 6-10 L/min, to maintain a SpO₂ level between 92-98%. Those who sustained the SpO₂ >92% in the ambient oxygen concentration were weaned off St-FMOT.

5.2 Experimental Arm: Children in the high-flow group received heated and humidified high-flow oxygen at a rate of 2 L*kg/min (maximum 25 L/min), using an age-appropriate Optiflow Junior cannula and Airvo 2 high-flow system (Fisher and Paykel Healthcare). The initial FiO₂ was set at

40%. The starting flow rate continued for a minimum of 4 hours. According to the patients' clinical response, the flow rate was decreased by 0.5 L*kg/min per hour. The FiO₂ was adjusted to obtain the SpO₂ levels between 92-98%. When the flow rate was at 0.5 L*kg/min, and the FiO₂ was equal to the ambient oxygen concentration, HFNCOT was stopped.

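### The plan gives no rule for how a child without a recorded recovery time enters the Mann-Whitney tests of the three primary outcomes

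*Combined protocol and SAP*

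**What the plan says.** **Outcomes and test.** Section 2.2 defines three primary outcomes, each a median time in hours: to an HR normal for age, to an RR normal for age, and to a one-class fall in CRS. Section 7.2 tests them: "Between groups, we will use the Mann-Whitney-U test for comparing the time of success for HR, RR, and CRS".

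**Who enters.** Section 7.2 says "We will perform intention-to-treat and per-protocol approaches for all outcomes" and then "The time of success for HR, RR, and CRS outcomes will be analyzed using the PP approach". The closing Statistical Analysis Plan paragraph promises both approaches only if necessary. None of these sentences covers a child who never reaches the event.

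**When readings stop.** The schedule runs from 1 h to 96 h, with the note "If the patient was not discharged after 96 hours, the procedures mentioned above were continued". The case report form (Appendix 4) has rows at admission, 1, 2, 4, 12 and 24 h, then daily from day 2 to day 10. It has no discharge row. The only later contact is a telephone call (Section 4.2: "An investigator will attend telephone follow-up on the first working day after the infant is 15 days post-discharge"), which yields no HR, RR or CRS.

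**What precedes discharge.** No discharge criterion is given. Section 5.1 says of mask oxygen: "Those who sustained the SpO₂ >92% in the ambient oxygen concentration were weaned off St-FMOT". It allows flow to be reduced once observations are stable or falling, which is not the same as normal.

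**Censoring.** Section 3.4 censors withdrawn children at withdrawal. No other censoring rule appears.

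**The concern.** A time-to-event outcome observed only in hospital leaves some children with a lower bound instead of a time whenever discharge can come before the event. A standard Mann-Whitney test has no place for a lower bound. The analyst must drop the child, enter some other time, or assign a rank, and the plan does not say which.

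The choice can change the primary result. If recovery is slower in one arm, more children in that arm will tend to lack a recorded time. Dropping them removes late recoveries mainly from that arm and pulls the two groups together. If stay differs by arm (length of stay is a secondary outcome), the arm discharged earlier keeps mostly its fast recoveries, and a difference can appear where there is none. The trial is open-label (Section 3.6), which is a further reason to fix the rule before results are seen.

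**Working it through.** **1. The plan's own figures (Section 7.1).** Attrition: 100 × 1.10 = 110, as stated. Dividing instead gives 100 / 0.90 = 111.1, or 112 in two equal arms, which is close enough. The base totals of 100, 38 and 43 cannot be reproduced, because no effect size or SD is given. They can be inverted. At two-sided alpha 0.05 and 80% power, the normal approximation is d = (1.960 + 0.842) × √(1/n₁ + 1/n₂).

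| Outcome | n₁, n₂ | d, normal | d, exact t-test |
|---|---|---|---|
| CRS | 50, 50 | 2.802 × 0.200 = 0.560 | 0.566 |
| HR | 22, 21 | 2.802 × 0.305 = 0.855 | 0.875 |
| RR | 19, 19 | 2.802 × 0.324 = 0.909 | 0.934 |

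**2. First illustration: effect implied for CRS, equal stay.** Assumptions: 55 per arm, log-normal recovery with log SD 0.8, shift 0.566 SD, the same independent discharge distribution in both arms, 4,000 simulated trials per row. The true median ratio is exp(−0.566 × 0.8) = 0.64. With all times known, power is 81–82%.

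| Controls unrecovered | Power, dropped | Power, discharge time entered | Power, worst rank | Median ratio, dropped |
|---|---|---|---|---|
| 2% | 79% | 81% | 81% | 0.65 |
| 5% | 77% | 82% | 82% | 0.66 |
| 10% | 72% | 81% | 81% | 0.68 |
| 20% | 63% | 79% | 79% | 0.70 |
| 30% | 54% | 75% | 78% | 0.73 |

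With no true effect and 20% unrecovered in both arms, the false-positive rate is about 5% whichever way these children are handled. In the 20% row about 9% of the high-flow arm is also unrecovered, so 0.20 × 55 + 0.09 × 55 ≈ 16 children lack a time. The attrition allowance is 110 − 100 = 10.

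**3. Second illustration: the protocol's reading times.** Assumptions: 55 per arm, log-normal recovery (log SD 1.0) and stay (log SD 0.4), correlation of the logs 0.3. Recovery counts at the first scheduled reading at or after the true time, and only if that reading precedes discharge. Scenarios (a) to (c) have median stay 72 h in both arms and effects of ln(43/24) = 0.58, ln(21/12) = 0.56 and ln(63/36) = 0.56 log SD. Ranges are from repeated runs of 1,200 to 4,000 trials.

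| Scenario | No recorded recovery | Dropped | Last reading entered | Log-rank, censored at last reading |
|---|---|---|---|---|
| (a) recovery 24 vs 43 h | 18%, 38% | 37–41% | 63% | 78–79% |
| (b) 12 vs 21 h | 5%, 15% | 58–60% | 75% | 76% |
| (c) 36 vs 63 h | 31%, 53% | 24–26% | 43% | 74–76% |
| (d) 24 h in both, stay 60 vs 84 h | | 12–15% (false positive) | 14% | 4–5% |

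Worst-rank Mann-Whitney gave 81–82% power in (a) and a 7% false-positive rate in (d). With recovery at 12 h in both arms and the stays of (d), dropping gave 5–6%, although one shorter repeat gave 8.5%. With correlation 0.6, power in (a) was 33% dropped against 82% log-rank, and the false-positive rate in (d) was 14–15% against 6%.

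**The case against.** **The plan does not say that these children are excluded.** A reader might infer that it does, since a child without success has no time of success. But the plan is silent. Section 7.2 also promises an intention-to-treat analysis for all outcomes, and Section 3.4 keeps withdrawn children in. This stands: dropping is an inference. The silence remains, and entering the last reading, the other natural choice, also loses power in the second illustration.

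**The children affected need not be the slowest, nor all three outcomes equally affected.** A child sent home early is not necessarily a slow recoverer. CRS needs only a one-class fall, so a child without that event leaves in the entry class or worse. Nothing suggests that this is common. This stands.

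**The power loss is shown at the CRS effect.** With the larger effects implied for HR and RR, power after dropping is 90% and 92% when baseline median recovery is 12 h, and 65% and 67% at 24 h. With recovery log SD 0.6 and the same standardised effect, (a) becomes 58% against 77%. This also stands: a negligible loss fits the documents as well as a large one.

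**The weaning rules might seem to make discharge differ by arm.** One could read Section 5.1 as ending mask oxygen on saturation alone while high flow depends on HR, RR and CRS. The text does not support this. The sentence on observations is not limited to high flow, the high-flow stopping rule names no HR, RR or CRS value, and stopping oxygen is not discharge (Section 2.3 measures the two separately).

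**The biostatistician is blinded to allocation.** This limits the scope for a choice driven by results, but it does not supply the rule.

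**Conclusion.** The gap is real and concerns all three primary analyses: times to an event, readings that end at discharge, no stated link between discharge and recovery, and a test that cannot take a censored time, with no rule for children who have none.

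The size cannot be fixed from the documents. On the assumed distributions, dropping these children leaves power between about 79% (2% of controls unrecovered) and about 25% (about half unrecovered), against about 75–82% when all are kept. The loss is probably smaller for CRS. Entering a substitute time ranges from almost harmless (discharge time, first illustration) to costly (last daily reading, second illustration).

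A generally inflated false-positive rate should not be inferred. With equal discharge patterns it stays near 5%. Inflation needs stay to differ by arm: 12–15% after dropping at 60 against 84 h, but only 7.1% (log-rank 5.4%) at 66 against 78 h. The documents give no evidence that stay will differ, only that it is an outcome of interest.

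**What to change.** In Section 7.2, keep every allocated child in each primary time and state one of these as primary and the other as sensitivity:

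- Mann-Whitney, with every child who has no recorded recovery ranked, tied, after the longest observed time. This keeps the planned test.
- Kaplan-Meier medians with a log-rank test, such children being censored at their last reading.

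Say explicitly how withdrawals censored under Section 3.4 enter each analysis, and reconcile the sentences on intention-to-treat and per-protocol sets for these outcomes. Report, for each outcome and arm, the number without recorded recovery. Add a discharge row for HR, RR and CRS to the case report form, so that recovery after the last daily reading is not lost.

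The cost is wording and one form row, with no extra patients. There are statistical downsides to state. Medians may be less favourable or not reached. The log-rank test treats discharge as non-informative: at a correlation of 0.85 between recovery and stay, its false-positive rate in (d) was 7.6%. Worst rank can be slightly anti-conservative if stay differs by arm (7% in (d)).

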7.3 Statistical Analysis Plan.....	21
8. REGULATORY CONSIDERATIONS.....	21
8.1 Participant Consent.....	22
8.2 Ethical Review.....	22
8.3 Sponsor.....	22
9. STUDY ADMINISTRATION.....	22
9.1 Protocol Deviations.....	22
9.2 Monitoring and Auditing.....	23
9.3 Study Documentation and Records Retention.....	23
9.4 Publication and Use of Study Findings.....	24
10. APPENDICES.....	25
11. REFERENCES.....	33

ABBREVIATIONS

AE	Adverse event
CI	Confidence interval
CPAP	Continue positive airway pressure
CRF	Case report form
CRS	Clinical respiratory score
ED	Emergency department
EUMF	Ege University Medical Faculty
FiO ₂	Fraction of inspired oxygen
FLUA	Influenza A
HR	Heart rate
HREC	Human Research Ethics Committee
HFNCOT	High-flow nasal cannula oxygen treatment
HRV	Human rhinovirus
IMV	Invasive mechanical ventilation
IND	Investigational new drug
IPPV	Intermittent positive pressure ventilation
LOS	Length of hospital stay
LOOT	Length of oxygen treatment
MD	Mean difference
NICE	National Institute for Health and Clinical Excellence
mPCR	Multiplex polymerase chain reaction
PEEP	Positive end-expiratory pressure
PEWS	Pediatric early warning score
ICU	Intensive care unit
PPU	Pediatric Pulmonology Unit
RCT	Randomised controlled study
RR	Respiratory rate
RSV A/B	Respiratory syncytial virus
SO ₂	Peripheral oxygen saturation
SOT	Standard oxygen treatment
St-FMOT	Standard face mask oxygen treatment
USA	United States of America
VBG	Venous blood gases

DEFINITIONS

Children

- ✓ In this study, is a child under the age of 24 months

Moderate and Severe bronchiolitis

- ✓ Defined as per CRS reported by Liu and colleagues (Appendices 1)
- ✓ Mild bronchiolitis: 0-4 point
- ✓ Moderate bronchiolitis: 5-8 point
- ✓ Severe bronchiolitis: 9-12 points

Supplemental Oxygen Requirement

- ✓ Peripheral capillary oxygen saturation (SpO_2) $<92\%$ while breathing room air

Standard Face Mask Oxygen Treatment (St-FMOT)

- ✓ The gas flow between 6.0 and 10.0 L/min

Rescue Treatment for St-FMOT

- ✓ First-tier, HFNCOT (2 L*kg/min) in the general ward
- ✓ Second-tier, admission to ICU for IMV

High-Flow Nasal Cannula Oxygen Treatment (HFNCOT)

- ✓ The gas flow at 2 L*kg/min or maximum 25 L/min

Rescue Treatment for HFNCOT

- ✓ Admission to ICU for IMV

STUDY SYNOPSIS

Title Comparison of high-flow nasal cannula and standard face mask oxygen therapy in children with moderate and severe bronchiolitis: A randomized controlled trial.

Trial Registry NCT04245202

Study Objectives

A. Primary Objectives

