3.6 Enrolment/Randomisation

During the clinical and eligibility assessment, and after obtaining written informed consent, we will apply nasal cannula wall oxygen at 2 L/min if a child needs supplemental oxygen. After written informed consent, the physician assigned the participants to either St-FMOT or HFNCOT by using simple randomization. On even-numbered days, patients received the St-FMOT, while on odd-numbered days received the HFNCOT. This trial is an open study because of the inability to blind clinicians, parents, or investigators to the two interventions.

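### No baseline covariate or stratum is stated; baseline-adjusted visit-wise HR and RR differences and a stratified test of CRS time would be cheap improvements, not corrections of an error.

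*Combined protocol and SAP*

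**What the plan says.** - **Primary times (section 7.2).** "Between groups, we will use the Mann-Whitney-U test for comparing the time of success for HR, RR, and CRS". No stratum or covariate is named. The same section assigns the times to success to the per-protocol approach.
- **CRS success (section 2.2).** It is a drop of one severity category: severe to moderate, or "from moderate [scores of 5-8] to mild [scores of 0-4] bronchiolitis (hour"). The Definitions give the bands 0-4, 5-8 and, at the top, "Severe bronchiolitis: 9-12 points".
- **HR and RR over time (section 7.2).** The method is "linear mixed models in which subjects will be included as random effects". The fixed effects are not listed.
- **Visit-wise comparisons (section 7.2).** They run only if the interaction has P < .1. Then "groups will be compared at baseline and following time points (the baseline was subtracted from these time points").
- **Secondary target (section 2.3).** "The mean difference in HR decreased compared with the baseline value from randomization to 96 hours (or to discharge"), with parallel wording for RR and CRS.
- **Sample size (section 7.1).** At 80% power and alpha 0.05, "the sample size yielded a total of 100 participants for CRS, 38 for RR, and 43 for HR".
- **Allocation (section 3.6).** "On even-numbered days, patients received the St-FMOT, while on odd-numbered days received the HFNCOT". No balancing on severity is stated.

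**The concern.** Baseline enters the plan as a value to compare and a value to subtract, but not as a stated covariate or stratum.

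For CRS time, the endpoint definition makes the task unequal. A child starting at 5 or 9 succeeds after losing one point, while a child starting at 8 or 12 must lose four. If starting score predicts time, an unstratified test leaves that variation in the noise and lets chance imbalance in starting scores move the comparison. CRS is also the outcome that set the sample size.

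For HR and RR, subtracting baseline over-corrects whenever the regression slope of the visit value on baseline is below 1. This costs precision and favours the arm that happened to start higher.

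**Working it through.** **1. The plan's own figures.** 100 x 1.10 = 110, the stated total. The 100, 38 and 43 cannot be rebuilt because section 7.1 gives no effect size or SD. Solving the two-sided t-test backwards at 80% power gives the implied standardised effects, and from them the planned power at 50 per arm (roughly 110 less 10%):

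| Outcome | Stated total | Implied d | Power at 50 per arm | Power at 55 per arm |
|---|---|---|---|---|
| CRS | 100 | 0.566 | 80.0% | 83.7% |
| RR | 38 | 0.934 | 99.6% | 99.8% |
| HR | 43 (22+21) | 0.875 | 99.1% | 99.5% |

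Only CRS has no spare power.

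**2. Points to fall.** Moderate: score minus 4. Severe: score minus 8. So 5 or 9 needs 1 point; 6 or 10 needs 2; 7 or 11 needs 3; 8 or 12 needs 4. The spread is the same inside both categories, so stratifying by severity category alone would not remove it.

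**3. CRS time, Mann-Whitney against van Elteren (all inputs assumed).** 50 per arm, the per-protocol set taken as a random subset. Time = m x (points/2)^a x exp(s x Z), with Z standard normal, read at the scheduled visits. m = 6, 12 or 24 h; s = 0.7 or 1.0; baseline scores uniform on 5-12 or weighted towards moderate. The effect is set so that Mann-Whitney has about 80% power.

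| How time depends on points | Van Elteren power | Change |
|---|---|---|
| Proportional (a = 1) | 85.9-92.7% | +6.3 to +12.1 |
| Square root (a = 0.5) | 80.2-83.5% | +0.2 to +2.9 |
| Not at all (a = 0) | 77.5-79.0% | -1.6 to -1.9 |

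If severe children are also 1.5 times slower (m = 12), the first two rows become +4.9 to +11.3 and -0.6 to +2.6.

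With no treatment effect, both tests reject in 4.8-5.2% overall. In the fifth of trials with the largest imbalance in points to fall (0.28 or more), Mann-Whitney rejects in 9.1-13.3% (a = 1) or 6.0-7.7% (a = 0.5). The remaining trials offset this at 2.9-3.9% or 4.2-4.8%. Van Elteren stays at 4.6-5.5% in both groups of trials.

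**4. HR and RR at a visit.** With r the baseline-to-visit correlation and k = SD(baseline)/SD(visit), ANCOVA variance / change-score variance = (1 - r²)/(1 + k² - 2rk). At k = 1 this is (1 + r)/2:

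| r | Variance ratio | ANCOVA power if change score has 80% (50 per arm) |
|---|---|---|
| 0.3 | 0.91/1.40 = 0.65 | 93.5% |
| 0.5 | 0.75/1.00 = 0.75 | 89.9% |
| 0.7 | 0.51/0.60 = 0.85 | 86.0% |
| 0.9 | 0.19/0.20 = 0.95 | 82.0% |

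For r 0.3-0.7, the ratio is 0.85-1.00 at k = 0.7 and 0.50-0.63 at k = 1.25. A chance baseline difference at the 1.96 SE limit is 1.96 x sqrt(2/50) = 0.392 SD. With equal SDs it moves the change-score difference by (1 - r) x 0.392 = 0.27, 0.20 and 0.12 SD at r = 0.3, 0.5 and 0.7.

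**5. The interaction gate.** Take a constant 0.5 SD effect at all T post-baseline visits, 50 per arm, equal correlation r. With baseline as a time point, the interaction F has non-centrality (50/2) x 0.5² x [T/(T+1)]/(1 - r), on T and 98T degrees of freedom. At P < .1:

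| T | r = 0.3 | r = 0.5 | r = 0.7 |
|---|---|---|---|
| 4 | 67% | 81% | 96% |
| 8 | 60% | 75% | 94% |

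Simulation gives 59-96%. If baseline leaves the response, the effect no longer varies across the modelled visits, the non-centrality is zero, and the group-by-visit term rejects at its null rate of about 10% (9-11% simulated). The gate therefore has to stay with the planned model.

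**The case against.** The strongest objection is that nothing here is wrong. Both tests keep their error rate under random allocation, change from baseline is what section 2.3 asks for, and the HR and RR comparisons are secondary and conditional. That stands, and it limits the point to an improvement.

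The size is also uncertain. The documents give neither r nor any link between starting score and time. The large CRS gains need time proportional to points, and the strata treat a 5 like a 9, which is an analyst's choice. Visits at 1, 2 and 4 h may correlate with baseline above 0.7, where the saving shrinks. The 0.392 SD imbalance is reached in only about 5% of randomised trials. All of this stands.

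The HR and RR times may also depend on distance from normal at baseline, and the subtraction sentence appears to cover CRS as well. Spare power answers the precision argument for the two times, but not the argument about chance imbalance. No change to either is proposed here.

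Timing matters too. The trial is open, several sections are in the past tense, and the last revision is dated 14/02/2021. A new primary test may no longer be possible.

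A reader might infer that the model certainly omits baseline. The text supports only that no such term is stated.

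**Conclusion.** The point holds as a low-cost improvement. For HR and RR, baseline adjustment saves 15-35% of variance at r 0.3-0.7 and about 5% at r 0.9 with equal SDs (0-50% for r 0.3-0.7 if the SD ratio k runs from 0.7 to 1.25). It estimates the same mean difference in change, because at a given baseline a difference in value is a difference in change. For CRS time, the change in power runs from about +12 points through roughly 0 to +3 to about -2, entirely on assumed inputs.

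Three stronger readings are not supported. The planned tests do not inflate type I error overall: the excess in imbalanced trials is offset in the others. The stratified test is not shown to be better for this trial, since its advantage depends on an unstated relation. Adjustment also does not repair even/odd-day allocation or the per-protocol restriction: selection from either can involve factors other than baseline HR, RR or CRS, and the 5% figures above assume random allocation and a random per-protocol subset.

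**What to change.** **HR and RR.** Keep the planned mixed model, with baseline as a time point, for the P < .1 interaction test. When that test opens the visit-wise step, take the group differences from ANCOVA at each visit, or from a mixed model of post-baseline values with group, visit, group-by-visit, baseline and baseline-by-visit terms and a random subject effect. State that the group-by-visit term of this second model is not the gate.

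**CRS time.** Add a van Elteren test stratified by baseline points above the target category (1, 2, 3, 4). Make it primary only if this is fixed before outcomes are seen by arm; otherwise report it as a sensitivity analysis beside Mann-Whitney. Keep the medians (IQR).

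**Cost.** SAP wording, one further PROC MIXED model (or ANCOVA at each visit), and one PROC FREQ step (CMH2 with SCORES=MODRIDIT). SAS is already named in section 7.2. Baseline HR, RR and CRS are already collected (Schedule of Observations and Procedures; Appendices 4), so no patients, visits or data are added. The downside is about 2 points of power on CRS time if the starting score does not predict it and the stratified test is made primary.
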